9.2.3.2 Safety assessment methods

9.2.3.2.1 Hypoglycemia

Hypoglycemia will be analyzed as incidence of patients (%) with at least one hypoglycemia event and number of hypoglycemia event per patient year of exposure.

Hypoglycemia events will be categorized (3, 4, 5) as follows:

• Severe hypoglycemia: Severe hypoglycemia is an event requiring 3rd party assistance of another person to actively administer carbohydrate, glucagon, or other resuscitative actions. These episodes may be associated with sufficient neuroglycopenia to induce seizure, unconsciousness or coma. Plasma glucose measurements may not be available during such an event, but neurological recovery attributable to the restoration of plasma glucose to normal is considered sufficient evidence that the event was induced by a low plasma glucose concentration. The definition of severe symptomatic hypoglycemia includes all episodes in which neurological impairment was severe enough to prevent self-treatment and which were thus thought to place patients at risk for injury to themselves or others. Note that "requires 3rd party assistance" means that the patient could not help himself or herself. Assisting a patient out of kindness, when assistance is not required, should not be considered a "requires assistance" incident.

Severe hypoglycemia will be qualified as an SAE only if it fulfills SAE criteria. All events of seizure, unconsciousness or coma must be reported as SAEs.

• **Documented symptomatic hypoglycemia**: Documented symptomatic hypoglycemia is an event during which typical symptoms of hypoglycemia are accompanied by a measured plasma glucose concentration of (≤3.9 mmol/L (≤70 mg/dL) (3). Clinical symptoms that are considered to result from a hypoglycemic episode are, eg, increased sweating, nervousness, asthenia/weakness, tremor, dizziness, increased appetite, palpitations, headache, sleep disorder, confusion, seizures, unconsciousness, or coma.

- **Asymptomatic hypoglycemia**: Asymptomatic hypoglycemia is an event not accompanied by typical symptoms of hypoglycemia but with a measured plasma glucose concentration less than or equal to 3.9 mmol/L (70 mg/dL).

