2.4.5.1 Analyses of Hypoglycemia

All analyses of hypoglycemia will be performed on the safety population and for the T1DM patients (except for analyses monthly, by time of the day and by subgroup), separately on events occurring during the main 6-month on-treatment period and during the 12-month on-treatment period (as defined in Section 2.1.4).

Incidence of patients with at least one hypoglycemia

- Incidence of patients with at least one hypoglycemia will be presented by treatment group for any hypoglycemia and for each hypoglycemia category (as described in Section 2.1.4.1).
- For any hypoglycemia, severe and documented symptomatic hypoglycemia category, incidence of patients with at least one hypoglycemia will be compared for SAR341402 versus NovoLog/NovoRapid using a logistic regression method. The model will include fixed-effect terms for treatment group, the randomization strata of geographical region and type of diabetes (Europe T1DM, US T1DM, US T2DM, Japan T1DM), screening HbA1c (<8%, ≥8%), and prior use of NovoLog/NovoRapid (Yes, No). If the logistic model does not converge (e.g., due to sparse data), randomization strata may be adapted or removed from the model. Odds-ratios and 95% CIs will be displayed using forest plots.
- Incidence of patients with at least one severe hypoglycemia will be summarized by symptom.
- The number of severe hypoglycemia and the number of documented symptomatic hypoglycemia <3.0 mmol/L (54 mg/dL) per patient will be summarized by treatment group.
- For any hypoglycemia, severe and documented symptomatic hypoglycemia category, incidence of patients with at least one hypoglycemia will be summarized by time of the day. Histograms will be provided.
- For any hypoglycemia, severe and documented symptomatic hypoglycemia category, incidence of patients with at least one hypoglycemia will be presented by subgroup and compared between SAR341402 and NovoLog/NovoRapid using a similar logistic regression model as described above, with added fixed-effect terms for the subgroup and the subgroup-by-treatment interaction. When the subgroup considered will be equal (or close) to one of the randomization strata, this randomization stratum will be removed from the model. Odds-ratios and 95% CIs will be presented across subgroups using forest plots. The significance level of the subgroup-by-treatment interaction will be also provided for descriptive purpose. The following subgroups will be displayed:

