- For any hypoglycemia, severe and documented symptomatic hypoglycemia category, number and rate of hypoglycemia per patient-year will be compared for SAR341402 versus NovoLog/NovoRapid using an overdispersed Poisson regression model with a log-link function, and the logarithm of the treatment-emergent period as offset (using PROC GENMOD). The dispersion parameter will be estimated by Pearson's chi-square statistic divided by its degrees of freedom (option SCALE=PEARSON). The model will include fixed-effect terms for treatment group and randomization strata of geographical region and type of diabetes (Europe T1DM, US T1DM, US T2DM, Japan T1DM), screening HbA1c (<8%, ≥8%), and prior use of NovoLog/NovoRapid (Yes, No). If a model does not converge (eg, due to sparse data), the randomization strata may be adapted or removed from the model. Rate ratios and 95% CIs will be displayed using forest plots.

• For any hypoglycemia, severe and documented symptomatic hypoglycemia category, the number and rate of hypoglycemia per patient-year will be presented by subgroup type of comparator (NovoLog, NovoRapid) and compared between SAR341402 and NovoLog/NovoRapid using a similar overdispersed Poisson regression model as described above. If a model does not converge (eg, due to sparse data), the randomization strata may be adapted or removed from the model. Rate ratios and 95% CIs will be displayed using forest plots.

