Exploratory analyses will be performed by subgroups defined by baseline and screening factors.

The following subgroups will be displayed:

- Race (American Indian or Alaska Native, Asian, Black or African American, Native Hawaiian or Other Pacific Islander, White, More than One Race, Unknown or Not Reported),
- Ethnicity (Hispanic or Latino, Not Hispanic or Latino, Unknown /Not Reported),
- Age group (<65, \geq 65 to <75, \geq 75 years of age),
- Sex (male, female),
- Baseline BMI (<30, ≥ 30 kg/m²),
- Baseline estimated GFR categories ($<60, \ge 60 \text{ mL/min}/1.73 \text{ m}^2$),
- Randomization stratum of type of diabetes (T1DM, T2DM),
- Randomization stratum of screening HbA1c (<8%, $\geq8\%$),
- Randomization stratum of prior use of NovoLog/NovoRapid (Yes, No),
- Type of comparator (NovoLog, NovoRapid),
- Regions (North America, Western Europe, Eastern Europe, ROW),
- Duration of diabetes ($<10, \ge 10$ years),
- Anti-SAR341402/NovoLog/NovoRapid antibody status at baseline (Positive, Negative).

Further subgroup analyses may be performed if deemed necessary for interpretation of results.

Relationship between immunogenicity endpoints and efficacy/safety assessments

Subgroup analyses and scatterplots will be conducted to assess the relationship between immunogenicity endpoints and efficacy/safety assessments.

The following efficacy/safety assessments will be summarized by treatment-emergent AIA (Yes, No) and treatment-emergent AIA at last on-treatment value (Yes, No):

- Primary efficacy endpoint (change in HbA1c from baseline to Week 26) (for the main 6-month analyses) and change in HbA1c from baseline to Week 52 (for the 12-month analyses): same statistical model as described in Section 2.4.4.1.4 for subgroup analyses will be performed.
- Hypoglycemia (any, severe, documented symptomatic): the proportion of patients with at least one event will be compared between treatment groups using the same statistical model as described in Section 2.4.5.1 for hypoglycemia subgroup analyses. The number of severe hypoglycemia and the number of documented symptomatic hypoglycemia <3.0 mmol/L (54 mg/dL) per patient will also be displayed for each treatment group.
- Common TEAEs: descriptive statistics by primary SOC, HLT, and PT, showing number (%) of patients sorted by SOC internationally agreed order. The other levels (HLT, PT) will be presented in an alphabetic order.

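### Apart from type of comparator, hypoglycemia by subgroup and by antibody status is compared between treatments only as at least one event, which says little if most patients have one

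*SAP*

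**What the plan says.** SAP 2.4.5.1 has two blocks.

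- **Incidence.** For any, severe and documented symptomatic hypoglycemia, "incidence of patients with at least one hypoglycemia will be presented by subgroup and compared between SAR341402 and NovoLog/NovoRapid using a similar logistic regression". This regression adds subgroup and subgroup-by-treatment terms. Twelve factors are listed: race, ethnicity, age, sex, BMI, eGFR, type of diabetes, screening HbA1c, prior NovoLog/NovoRapid, type of comparator, region and duration of diabetes. "The significance level of the subgroup-by-treatment interaction will be also provided for descriptive purpose".
- **Rate.** Overall event rates are compared "using an overdispersed Poisson regression model with a log-link function, and the logarithm of the treatment-emergent period as offset", with the dispersion taken from the Pearson statistic. For subgroups this model appears once: "number and rate of hypoglycemia per patient-year will be presented by subgroup type of comparator (NovoLog, NovoRapid) and compared between SAR341402 and NovoLog/NovoRapid". That bullet does not mention an interaction term.

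The section opens with "All analyses of hypoglycemia will be performed on the safety population and for the T1DM patients", but excludes subgroup analyses from the T1DM repeat. The overall rate model is therefore also run in T1DM patients.

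SAP 2.4.5.7 covers antibody status. By treatment-emergent AIA, "the proportion of patients with at least one event will be compared between treatment groups using the same statistical model" as the subgroup analyses of 2.4.5.1. The same parameters are summarized by baseline AIA status. Three descriptive displays sit beside this:

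- per-patient counts of severe events and of documented symptomatic events below 3.0 mmol/L;
- yearly rates of those two categories plotted against peak titer;
- listings of hypoglycemia for patients with treatment-emergent AIAs and outlying titers.

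Protocol 9.2.3.2.1 defines hypoglycemia both as incidence and as "number of hypoglycemia event per patient year of exposure". SAP 2.4.5 describes the safety analyses as essentially descriptive.

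**The concern.** Every patient is on multiple daily injections and measures glucose often. Under Protocol 9.2.2.2.3, each transferred reading of 3.9 mmol/L or below prompts the episode diary, with or without symptoms. The any category in SAP 2.4.5.1 also takes in probable and relative events. Most patients may therefore have at least one event within 26 weeks, and more will over 52. Once nearly everyone is a yes, the analysed variable barely moves when the event rate changes.

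Two uses of the results are affected. The subgroup forest plots would be read as evidence of consistency. The antibody splits serve a stated secondary objective, the relation of AIAs to safety. In both, an odds ratio near 1 or a large interaction p-value could reflect the ceiling and not similarity.

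The logistic model also ignores length of exposure. Two patients without an event count the same whether they were followed for 4 weeks or 26.

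**Working it through.** **Plan's own figure.** There is none for hypoglycemia. The power statements in SAP 1.3 concern HbA1c and AIA incidence only.

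**Inputs from the documents.** 290 patients per arm, so half is 145 per arm. T2DM about 100, so 50 per arm. T1DM about 480, so 240 per arm. AIA incidence 15 to 20% in earlier studies; at 20%, 0.20 × 290 = 58 per arm. Main period 26 weeks, taken as 0.5 year.

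**Assumed inputs.** Comparator rate 0.1 to 40 events per patient-year, gamma-Poisson counts with dispersion k = 1 to 2, rate ratio 1.5 unless stated, two-sided 5%, no stratum covariates.

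**Formulas.** With mean count m = rate × 0.5 and n patients per arm:

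- P(at least one event) = 1 − (1 + k·m)^(−1/k)
- Yes/no: SE of log odds ratio = √[1/(n·p0·(1−p0)) + 1/(n·p1·(1−p1))]
- Rate: SE of log rate ratio = √[(1/m0 + k)/n + (1/m1 + k)/n]
- Power ≈ Φ(effect/SE − 1.96)

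**Worked case: n = 145, 20 per patient-year, k = 1.** m0 = 10 and m1 = 15.

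- p0 = 1 − 1/11 = 90.9%; p1 = 1 − 1/16 = 93.8%. A 50% excess of events moves the proportion by under 3 points.
- Yes/no: log odds ratio = ln(15/10) = 0.405; SE = √(1/11.98 + 1/8.50) = 0.449; power ≈ Φ(0.90 − 1.96) ≈ 15% (simulation 14%).
- Rate: log rate ratio = 0.405; SE = √[(1.100 + 1.067)/145] = 0.122; power ≈ Φ(3.32 − 1.96) ≈ 91% (simulation 91 to 93%).
- At 12 months (m = 20 and 30) the proportions are 95.2% and 96.8%, closer still to the ceiling.

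**Simulated power, 145 per arm, rate ratio 1.5** (ranges over k = 1 to 2):

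| Comparator rate per patient-year | Comparator patients with at least one event | Yes/no model | Rate model |
|---|---|---|---|
| 40 | 84–95% | 7–10% | 66–91% |
| 20 | 78–91% | 13–14% | 68–93% |
| 5 | 59–71% | 19–33% | 59–83% |
| 1 | 29–33% | 28–38% | 45–56% |
| 0.1 | about 5% | 10–12% | 10–12% |

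The rate model rejected a true rate ratio of 1.0 in 5.0 to 5.7% of runs.

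**Interaction tests at 20 per patient-year, rate ratio 2 in one level and 1 in the other, equal comparator rates in both.** Two equal subgroups: yes/no 16–18%, rate model 79–97%. AIA status with 20% positive: yes/no 6–11%, rate model 67–92%.

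**Which variance to use.** Under these counts the Poisson dispersion is 1 + k·m, so it grows with the rate. A joint interaction model with one Pearson scale averages it over levels. Take 240 against 50 per arm, k = 1 and no treatment effect:

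- Small group at a quarter of the large group's rate (10 against 40): dispersions 6 and 21, pooled (480×21 + 100×6)/580 = 18.4. The small group's SE is inflated by √(18.4/6) = 1.75.
- Small group at four times the rate (40 against 10): pooled (480×6 + 100×21)/580 = 8.6. The SE shrinks by √(8.6/21) = 0.64, giving a false-positive rate of about 2Φ(−1.96 × 0.64) ≈ 21%.

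Simulation agrees. With a single shared scale, power at rate ratio 1.5 in the low-rate small group is 2–9%, no better than the logistic model (about 8–14%). False positives in a small group with two to four times the rate are 12–23%. Fitting within each level, or using robust standard errors, brings error back to about 5–7% and power to about 26–47%.

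**The case against.** **What stands against the point.**

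- These analyses are descriptive. No power target or consistency criterion is attached to them, and Protocol 11.4.3.1 says only that odds and rate ratios may be provided.
- The whole size of the effect depends on assumed event rates, dispersion and rate ratio.
- Simply adding interaction terms to the specified Pearson-scaled model could mislead when rates differ between subgroup levels, as shown above. The fix has to deal with this.

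**Stronger readings that the documents do not support.**

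- A reader might infer that subgroup hypoglycemia is never modelled as a rate. It is, for type of comparator, and the overall rate model is repeated in T1DM patients.
- A reader might infer that counts are ignored by antibody status. They are displayed, and rates are plotted against peak titer. They are not modelled, and these displays do not cover any hypoglycemia or documented symptomatic events at the 3.9 mmol/L threshold.
- A reader might infer that patients who stop early are counted as event-free. An event before stopping still counts. The valid point is only that exposure time is ignored, and this matters less the more patients have an early event.
- A reader might expect an exposure offset to remove follow-up bias from the treatment-emergent AIA split. It does not: longer follow-up still gives more chances to be classified positive. Baseline AIA status does not have this problem.

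**Conclusion.** The point holds in limited form. For eleven of the twelve listed factors, the only between-treatment model comparing subgroup levels is yes/no. The same holds for both antibody splits, reading the baseline-status summaries as carrying over the same model.

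If 78 to 95% of comparator patients have an event, that model has about 7 to 14% power for a rate ratio of 1.5 with 145 per arm, against 66 to 93% for a rate model. A gain remains at 1 event per patient-year (28–38% against 45–56%) and vanishes at about 5% incidence, so severe hypoglycemia would not benefit if it is that rare. These figures rest on assumed rates, dispersion and rate ratio, since the documents give none.

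No confirmatory conclusion is at risk. What is at risk is the reading of apparent consistency across subgroups and across AIA status.

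**What to change.** 1. In SAP 2.4.5.1, for any and documented symptomatic hypoglycemia, extend the exposure-offset rate model to all listed subgroup factors. Report rate ratios with 95% CIs and a descriptive interaction test.
2. In SAP 2.4.5.7, do the same for treatment-emergent and baseline AIA status. Note beside the treatment-emergent results that classification depends on length of follow-up.
3. State the variance method: fit the overdispersed Poisson model separately within each subgroup level, or fit the joint model with robust (sandwich) standard errors. Do not use one Pearson scale across levels. Apply the same rule to the existing type-of-comparator analysis and state whether it has an interaction term.
4. Keep the logistic analysis as a companion display, and as the only model for severe hypoglycemia or where the rate model does not converge.

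The cost is SAP wording and further runs of a model already specified, with a variance option added. No new data are needed. The downside is more exploratory output, and wide intervals or non-convergence in very small subgroups. The SAP already allows strata to be adapted or dropped when the rate model does not converge.
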